### **12.1.3 Specimen Banking**

Once the study has ended, serum samples of subjects who did not agree to an additional blood collection for DNA analysis, banking, and future use will be anonymized by destroying the key linking Subject ID to subject identity. An aliquot will be sent to and banked at the NIH BioLINCC biorepository and will be managed per NIH Data sharing policies. This banking is not optional for subjects who agreed to participate in the

correlative studies (substudy). The remaining samples from these subjects will be destroyed. Serum samples sent to NIH will not be used for DNA analysis.

The serum and whole blood of correlative study subjects who agreed to the additional blood collection for DNA, banking, and future use will be similarly anonymized. If funding becomes available in the future, one aliquot of each anonymized sample will be shipped commercially to NIH for banking and future unspecified research, including genetic testing and GWAS. NIH may place resulting genetic data in its own Database of Phenotypes and Genotypes or share with other federal genetic data repositories. The rest of the anonymized samples from these subjects will remain at Brigham and Women's Hospital (for specimens from US sites) and at the Peter Munk Cardiac Centre (for specimens from Canadian sites) for future unspecified research, including genetic testing (if funding becomes available) and creation of cell lines.

### **12.2 ACHD Sub-study**

The ACHD sub-study will aim to recruit at least 500 patients of the total number of anticipated INVESTED subjects. Study procedures in the parent INVESTED protocol will be followed. No additional visits or procedures are required for this companion ACHD study. The ACHD case report form should be completed for each enrolled patient within 1 week following study registration. Patients previously randomized to and participating in the INVESTED trial may be retroactively entered on this sub study concurrent with registration for returning years 2 and 3. (Appendix B).

## **13.0 STATISTICAL CONSIDERATIONS**

### **13.1 Statistical Analysis Plan**

All statistical data analyses will be performed using SAS (SAS Institute, Inc., Cary NC) and R (R Foundation for Statistical Computing, Vienna, Austria. <http://www.R-project.org/>).

### **13.2 Analysis Population**

Because the effects of vaccination last for at least a calendar year, there will be no typical adherence issues with vaccination at enrollment. However, we expect some subjects will not be revaccinated according to randomization in subsequent influenza seasons. We will therefore employ a modified intention-to-treat (mITT) analysis in which subjects' clocks will be reset 2 weeks after influenza vaccination, and primary endpoint events will be counted until July 31 of that year. Each subject can therefore contribute primary endpoint events in each season they are vaccinated. Although a subject's experiences from year to year may be correlated, for simplicity, each subject's contribution for each enrolling season will be treated as independent. We will assess the independence of the primary endpoints from year to year in a sensitivity analysis as described in Section 13.4. The usual intent-to-treat (ITT) principle for the analysis of randomized controlled trials will be followed for the assessment of balance of baseline subject characteristics and reporting of adverse events and for recurrent events analyses described below in Sections 13.4 and 13.5.

### **13.3 Analysis of Baseline Characteristics**

We will assess the balance in the randomization groups with regard to subject characteristics including cardiovascular disease measures. The subjects will be compared on each characteristic between the randomized vaccine arms using methodology appropriate to the measure. More specifically, baseline subject characteristics will be summarized using descriptive statistics such as mean and standard deviation or median and interquartile range (IQR) for quantitative measurements and frequency and proportion for binary or categorical measurement and using graphics such as box plots and empirical distribution functions and assessed for balance between the two dose groups.


In order to assess the independence of the primary endpoints from year to year in individuals receiving influenza vaccines more than once, the frailty model version of the Cox proportional hazards regression will be evaluated. In case the independence assumption is not tenable, we will estimate intra-subject correlation from year to year using the method of Prentice and Cai.

### 13.5 Analysis of Secondary Endpoints

Secondary endpoints will include total (first and recurrent) cardiopulmonary hospitalizations or all cause-death during the subject's entire study participation duration, the composite of cardiovascular death or cardiovascular hospitalization within each enrolling season, the composite of all-cause death or cardiopulmonary hospitalization across all enrolling seasons, and individual components of the primary endpoint, including time to all-cause death and time to

first occurrence of cardiopulmonary hospitalization. Time to composite endpoints and times to individual components of the composite endpoints will be analyzed similarly as the primary endpoint in Section 13.4 with individual components of the composite endpoints that are non-terminating events analyzed using methods for competing risks. Recurrent events analysis will be performed for recurrent non-terminating events across all enrolling seasons. For all analyses, two-sided p-values < 0.05 will be considered statistically significant. In addition, the rate of cardiopulmonary hospitalization with death as competing risk will be analyzed using nonparametric and semi-parametric analyses based on the mean frequency function defined as the marginal mean of the cumulative number of cardiopulmonary hospitalizations over time subject to a terminal event of death.

### **13.6 Analysis of Safety Endpoints.**

The number and percentage of subjects experiencing influenza vaccine related adverse events (e.g. injection site reactions, systemic side effects including headache, myalgia, and fever) and SAEs will be summarized by system organ class and by treatment arm. The safety endpoints will be summarized using frequency and proportion and compared between the two dose groups using nonparametric methods such as chi-square or Jonckheere-Terpstra tests.

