10.4.1 Incidence of vaccine injection site reactions (described in section 11.0)

### 10.5 Secondary Safety Endpoints

10.5.1 Incidence of vaccine-related adverse events and serious adverse events

### 10.6 Correlative study endpoints

- 10.6.1 Immune Response Sub-Study (up to 3,000 subjects)**
- 10.6.1.1** Geometric mean titers post vaccination
  - 10.6.1.2** Change in antibody titers at 4 weeks post-vaccination from baseline
  - 10.6.1.3** Seroconversion, i.e. 4-fold rise in antibody concentrations from baseline to A/H1N1, A/H3N2, and B-type vaccine antigens
  - 10.6.1.4** Seroprotection, i.e. antibody titer levels  $\geq 1:40$  to the A/H1N1, A/H3N2, and B-type vaccine antigens 4 weeks following influenza vaccination. Seroconversion and seroprotection to A/H1N1, A/H1N3 strains and the B-Yamagata lineage.
- 10.6.2 ACHD Sub-Study**
- 10.6.2.1** Time to first occurrence of death or cardiopulmonary hospitalization within each influenza season in the ACHD population. (Appendix B)

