## 11.3 Time Period and Frequency for Event Assessment and Follow-Up

All adverse events temporally related (within 1 week) to vaccine administration will be collected on appropriate CRFs. Specific adverse events of interest (see section 11.4.4) will be queried.

All serious adverse events that are possible trial endpoints, including death and all hospitalizations, will be collected on appropriate endpoint collection forms. All other serious adverse events not covered by endpoint collection forms will be collected on appropriate SAE CRFs. CRFs will be completed at the time the event becomes known to study investigators, either by notification by the subject, or during influenza season surveillance, at which time

investigators will inquire about the occurrence of events since the last time of contact. Serious adverse events and trial endpoints (death or hospitalization) will be collected until July 31 of the influenza season.

All suspected unexpected serious adverse reactions (SUSARs) will be collected on appropriate CRFs during the course of the trial. All SUSARs will be collected at the time they are known to study investigators and may be subject to specific reporting requirements by health authorities or local IRBs.

Non-serious adverse events not temporally related to study vaccine administration (> 1 week) and not suspected to be related to study vaccine administration will be collected locally only, per GCP guidelines.

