## **11.4 Reporting Procedures**

### **11.4.1 Adverse Event Reporting**

All adverse events that occur within 1 week of study vaccine administration will be collected and specific adverse events of interest (see section 11.4.4) will be queried. Non-serious adverse events not temporally related to study vaccine administration (> 1 week) and not suspected to be related to study vaccine administration will not be collected.

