### **11.4.4 Adverse Events of Interest**

The following events occurring within one week of study vaccine administration are considered events of special interest and will be specifically queried:

- Injection site reactions (pain, redness, or swelling at injection site)
- Myalgia

- Fever
- Malaise
- Headache

The following important medical events will be considered SAEs and reported according to section 11.4.3:

- Guillain-Barré syndrome
- Bell's palsy
- Encephalitis/myelitis
- Optic neuritis
- Stevens-Johnson syndrome
- Toxic epidermal necrolysis

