### **13.19 Data and Safety Monitoring Board (DSMB)**

A Data and Safety Monitoring Board (DSMB) appointed by the NHLBI will monitor the study. The DSMB consists of individuals with expertise in cardiovascular diseases, influenza, clinical trial methodology, biostatistics, and bioethics. The DSMB will review and approve the protocol prior to subject enrollment.

Early stopping guidelines are specified in Section 13.11 on Interim Analysis. The DSMB may recommend stopping the study early if the incidence of adverse events in the high-dose arm is greater than in the standard-dose arm or if the formal interim analysis shows clear efficacy results. Formal stopping boundaries are not proposed for other endpoints besides the primary endpoint. However, the DSMB may recommend stopping the study for other reasons, taking into account the efficacy and safety data from this trial and other studies, or concerns about study conduct.

The DSMB chair will be notified of any serious adverse events considered probably or definitely related to the study treatment. The DSMB reviews data on adverse events, adverse drug reactions, data quality, and study recruitment at regular intervals (every 6 months), and makes recommendations about study conduct to the Executive Committee.

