8.9 Analysis of Safety Endpoints

The analysis of the safety endpoints will follow the mITT analysis used for the primary efficacy endpoints. The primary safety endpoint is incidence of vaccine injection site reactions such as injection site reactions (e.g. erythema, pain, or redness), and systemic side effects including headache, myalgia, and fever. The number and percentage of subjects experiencing vaccine injection site reactions will be summarized by treatment arm and by enrolling season, and the incidence will be compared using nonparametric methods such as chi-square tests. Incidence of vaccine injection site over multiple seasons will be considered independent.

The secondary safety endpoint is incidence of vaccine-related adverse events and serious adverse events and will be analyzed as above for the primary safety endpoint.

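### Apart from injection site reactions and SAEs, the arms are compared only on vaccine-related adverse events, an undefined class, although all adverse events within 7 days of vaccination are collected

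*Protocol*

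**What the plan says.** Collection is not filtered by cause. Protocol 11.3 states: "All adverse events temporally related (within 1 week) to vaccine administration will be collected on appropriate CRFs". Protocol 11.4.1 repeats this: "All adverse events that occur within 1 week of study vaccine administration will be collected". Protocol 11.4.4 adds a short list (injection site reactions, myalgia, fever, malaise, headache) under this rule: "The following events occurring within one week of study vaccine administration are considered events of special interest and will be specifically queried".

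The endpoints are narrower. The primary safety endpoint is injection site reactions (Protocol 10.4.1, SAP 4.3.1). The secondary one is "Incidence of vaccine-related adverse events and serious adverse events" (Protocol 10.5.1; SAP 4.3.2 adds that it applies within each enrolling season).

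The analyses follow the endpoints. Protocol 13.6 summarises by arm "The number and percentage of subjects experiencing influenza vaccine related adverse events", giving injection site reactions, headache, myalgia and fever as examples, and lists SAEs alongside. It then compares the dose groups with nonparametric tests. SAP 8.9 says "The secondary safety endpoint is incidence of vaccine-related adverse events and serious adverse events" and analyses it in the same way as the primary safety endpoint.

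Protocol 11.2.2 defines five levels of relationship to study agent. Neither document says which of them make an event vaccine-related for analysis.

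**The concern.** In a randomized, blinded comparison, the difference between arms in all adverse events already estimates the excess caused by the higher dose. No event needs an individual causal label for that. Classing events first and comparing only the related ones makes the estimate depend on how well the classing works. A reaction that high dose causes, but that is put down to something else, disappears from the comparison. In patients with a recent infarction or heart failure admission, non-specific symptoms have many other possible explanations.

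With no stated cut-off, two analysts could follow the SAP faithfully, one including possibly related events and the other not, and report different results for the same endpoint. Use of the high-dose vaccine below age 65 is described as investigational (Protocol 4.0), so an understated excess of reactions would matter to readers of the safety results.

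**Working it through.** The documents give no safety event rate, safety power or safety sample size, so there is no plan figure to reproduce. The check is mainly textual.

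**Step 1. What is collected against what is compared**

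| Event type | Collected | Compared between arms whatever the cause? |
|---|---|---|
| Injection site reactions | Yes, queried (11.4.4) | Yes: primary safety endpoint (Protocol 10.4.1, SAP 4.3.1 and 8.9) |
| SAEs | Yes (11.3, 11.4.2) | Yes on the natural reading of Protocol 13.6, which lists them separately; Protocol 10.5.1 and SAP 4.3.2 and 8.9 could be read as related SAEs only |
| Headache, myalgia, fever | Yes, queried | Not assured: Protocol 13.6 gives them as examples of vaccine-related events; SAP 8.9 names them when describing the primary safety endpoint, but its next sentence summarises and compares only injection site reactions |
| Malaise | Yes, queried | Not assured: named in neither Protocol 13.6 nor SAP 8.9 |
| Other non-serious events within 7 days | Yes (11.3, 11.4.1) | No: only if classed as vaccine-related |

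Neither document plans an arm comparison of all 7-day adverse events regardless of cause.

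**Step 2. Effect on the measured excess**

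Let b be the standard-dose event rate, d the true excess on high dose, s the share of the excess events classed as related, and f the share of background events classed as related. With raters blinded (Protocol 13.18.3), take s and f as independent of arm.

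- Unfiltered: rates b and b + d, so the difference is d.
- Filtered: rates fb and fb + sd, so the difference is sd.

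The background term cancels, and the excess shrinks by the factor s whatever f is.

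**Step 3. Effect on power (illustration; b, d, s and f are all assumed)**

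Take b = 10%, d = 2 points, n = 4,650 per arm (Protocol 13.12, one vaccination per subject) and two-sided 0.05. Power ≈ Φ(difference/SE − 1.96), with SE = √[(p₁(1−p₁) + p₂(1−p₂))/n].

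- Unfiltered: SE = √[(0.10×0.90 + 0.12×0.88)/4650] = 0.00649; 0.02/0.00649 − 1.96 = 1.12; power 0.87.
- Filtered, s = 0.5, f = 0.1 (1% against 2%): SE = √[(0.01×0.99 + 0.02×0.98)/4650] = 0.00252; 0.01/0.00252 − 1.96 = 2.01; power 0.98.

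| s | Measured excess (points) | Power, f = 0.1 | Power, f = 0.3 | Power, f = 0.5 |
|---|---|---|---|---|
| 0.75 | 1.5 | 1.00 | 0.97 | 0.87 |
| 0.5 | 1.0 | 0.98 | 0.75 | 0.56 |
| 0.25 | 0.5 | 0.58 | 0.27 | 0.19 |

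The measured excess falls in every row. Power runs from above to well below the unfiltered 0.87, depending on how much background the filter also removes.

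**The case against.** The strongest reply is that vaccine-related is simply the protocol's name for the diary reactions. Protocol 13.6 explains the term by example, and the examples are reactogenicity events. The schedule in Protocol 9.4 labels the baseline and week 1 assessments as assessments of vaccine-related reactions. Neither document says that the 11.2.2 rating defines the endpoint, or that every 7-day event is rated. This stands as far as it goes: a filter based on investigator ratings is an inference. But under this reading unsolicited events still go uncompared, and malaise is still named in neither analysis section. The ambiguity is itself a reason to define the term.

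Second, Protocol 13.2 and 13.17 speak of reporting adverse events without a relatedness limit, and SAP 1.3 calls adverse events and SAEs the safety endpoints. Those passages settle the analysis population and mention events only generically. They do not set out a comparison of all events.

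Third, the filter removes noise as well as signal, and investigators are blinded. Both points are right. A reader might infer that filtering only discards true cases and so must cost power; the table above shows otherwise. Blinding prevents ratings driven by knowledge of the arm, but it does not restore caused events that are classed as unrelated.

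A reader might also see a conflict with Protocol 13.19, under which the DSMB may recommend stopping "if the incidence of adverse events in the high-dose arm is greater than in the standard-dose arm", with no relatedness condition. Monitoring that is broader than the final tabulated endpoint is ordinary. The higher levels of relatedness named there trigger notification of the DSMB chair about SAEs; they do not define an endpoint.

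**Conclusion.** The point holds as a limited gap in the secondary safety analysis. Non-serious 7-day events other than injection site reactions have no assured arm comparison unless they are classed as vaccine-related, and that class has no stated cut-off. For the filtered events the measured excess is s times the true excess, provided that blinding keeps the classing the same in both arms. The size of s is unknown, and the documents give no event rates, so the figures above show direction and mechanism only.

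A reader might infer that all safety comparisons rest on causality judgements. The documents do not support that: injection site reactions are the primary safety endpoint with no causality condition, and Protocol 13.6 lists SAEs separately. Nor do they support a statement that the excess of headache, myalgia and fever will be understated by a known amount. SAP 8.9 can be read as placing these three under the primary endpoint; what is missing is a sentence that actually compares them. The change is worth making because it gives a better-defined comparison from data already collected.

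**What to change.** In Protocol 10.5.1 and 13.6 and SAP 4.3.2 and 8.9:

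1. Compare arms on all adverse events within 7 days of each vaccination regardless of causality, overall and separately for each event queried in Protocol 11.4.4, including malaise.
2. State that SAEs are counted whatever their cause.
3. Name the levels of the 11.2.2 scale that make an event vaccine-related, and show those events as a supportive subset.
4. In SAP 8.9, say whether headache, myalgia and fever belong to the primary or the secondary safety endpoint, and make the comparison sentence match.

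The cost is some wording and one extra table set, with no new data collection. The drawback is that reported absolute rates will rise because they include background illness, so the text should direct readers to the difference between arms.

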### **13.7 Analysis of Immune Outcomes (Correlative Study Endpoints)**

Antibody titers and other immune responses such as the incidence of seroconversion and seroprotection in A/H1N1, A/H3N2 and B-type vaccine antigens will be summarized with descriptive statistics such as mean and standard deviation or median and IQR for quantitative measures and frequency and proportion for qualitative measures for baseline and week 4 post-vaccination along with graphics such as bar plots and compared between the two treatment arms using two-sample tests. Clinical outcomes will be compared between those with and those without seroconversion and seroprotection in A/H1N1, A/H3N2 and B-type vaccine antigens using log-rank tests. Cox proportional hazards regression analysis will be performed for the primary endpoint of the composite of all-cause death or cardiopulmonary hospitalization with the geometric mean titer across vaccine strains post-vaccination as a model term, instead of individual antibody titers, to avoid issues of collinearity, stratified by influenza season, while adjusting for other covariates including treatment and other immune responses and the interaction between treatment and match for circulating B (Victoria)-lineage that is included only in the standard-dose QIV (binary), based on influenza typing and subtyping data. The hazard ratio for each doubling of the geometric mean titer will be estimated along with confidence intervals from Cox proportional hazards regression models. Given that the traditional definition of seroprotection, namely HAI titers  $\geq 40$ , may be an inadequate estimate of a protective threshold during years of poor match between vaccine antigens and circulating strains, we will also assess seroprotection defined as HAI  $\geq 80$ , 160, and 320 as exploratory analyses.

### **13.8 Additional Analyses**

In addition to the analysis of the clinical and immune outcomes, we will evaluate the association between antibody titers post-vaccination and subsequent hospitalizations using Poisson or negative binomial regression models to investigate the association of number of days in hospital per month on the log of the titers, controlling for treatment and other important covariates.

### **13.9 Subgroup Analysis**

Many baseline characteristics are known to be prognostic or suspected to be confounders for the clinical outcomes in the study population with high-risk cardiovascular disease. They include age, sex, race/ethnicity, smoking status, obesity (BMI $\geq 30$ ), baseline CV risk group (AMI vs HF), diabetes, renal dysfunction, and use of statin and beta-blocker medications. Influenza season is also known to affect the clinical outcome. Internal consistency of the primary analysis will be assessed in subgroups defined by these and other baseline characteristics. Heterogeneity of

efficacy will be assessed using interaction tests of treatment by each of these baseline covariates and by influenza season. Any interaction test resulting in a heterogeneity p-value < 0.10 will be further evaluated for clinical plausibility of effect modification.

